6.4 Cognitive Assessments

After participants complete the questionnaires, they will be asked to complete two cognitive assessments. We will also use the **Leeds Food Preference Questionnaire**, a computerized procedure to assess liking, wanting, and relative preferences for high versus low-fat foods and sweet versus savory foods.⁷⁶ The Leeds Food Preference Questionnaire assesses different components of food preference and food reward. Participants are presented with an array of pictures of individual food items common in the diet that are high or low in fat but similar in familiarity, protein content, sweet or non-sweet taste and palatability. The task takes approximately 10 minutes to complete. **Cognitive function** will be assessed with the NIH Toolbox Cognitive Function Battery which includes 7 tests covering different cognitive abilities including attention and executive functioning, episodic memory, working memory, language, and processing speed.⁷⁷ The cognitive assessments will be administered in a private room at both fMRI scans as well as a week 8 visit.

Week 8 Assessment.

We will also conduct a mid-point assessment. During this visit we will obtain participants' weight, cognitive assessments, and questionnaires as listed on Table 1 and Table 2. Given the restrictions with COVID, we will only use self-report weight and self-report questionnaires at the week 8 visit.

6.5 Wait-List Post-Treatment Visit (Wait-list Group Only)

After individuals in the WLC group complete their second fMRI assessment, they will be offered the WW treatment. The WLC group will be asked to complete questionnaires as well as their height, weight, and behavioral measures at their end of intervention visit.

6.6 Randomization Visit

Participants who meet all eligibility criteria assessed at the screening visit will be scheduled for a baseline fMRI assessment. The visit will occur within approximately 4 weeks of beginning treatment. They will be instructed to complete the self-reported outcomes either online (using a link e-mailed to them) or using paper-and-pencil questionnaires (for those who prefer this method) approximately 10 days before their fMRI scan. Their questionnaires will be reviewed for completeness at the fMRI visit, with any omissions or errors corrected. The randomization visit will include a weight, waist circumference, blood pressure, and heart rate, and completion of additional baseline assessments (as described in Table 2). Participants will then be randomly assigned to the two groups in equal numbers (i.e., 1:1 ratio). This will be accomplished using a computer-generated algorithm operated by faculty at the Center for Weight and Eating Disorders at the University of Pennsylvania (e.g., [name]). Assignment will be made from randomly varied block sizes (2 or 4). This is an open-labelled randomized trial. Due to COVID-19, we have combined the randomization visit with the baseline fMRI visit. After they complete their fMRI visit, they will be randomized to a treatment group.

CONFIDENTIAL

This material is the property of the University of Pennsylvania.

Table 1. Schedule of Study Assessments and Treatment Visits

	Weeks																																	
	8	9	10	11	12	13	14	15	16	17	18	19	20	21	22	23	24	25	26	27	28	29	30	31	32	33	34							
Screening																																		
FMRI Assessment																																		
Cognitive, Behavioral, and Self-report Assessments																																		
Randomization Visit																																		
WW Group Treatment																																		
WLC Group Treatment																																		

*WLC group only. For participants affected by COVID-19 and subsequent mandates necessary to help mitigate the transmission of the virus (e.g., stay-at-home orders), their fMRI assessments will occur at the end of the intervention. They will have questionnaire assessments administered at week 16 and then again at the end of the intervention when they can have their fMRI scan. The randomization visit will now be combined with the fMRI visit.

Table 2. Schedule of Procedures

Study Phase	Screening	Baseline FMRI Assessment ^{a,b}	Randomization Visit ^c	Intervention	Cognitive, Behavioural, and Self- report Assessments	Follow-up FMRI Assessment ^b
Informed consent	X					
Review inclusion/exclusion criteria	X					
Demographics	X					
Medical history	X					
Blood pressure, heart rate	X		X		X	
Height	X					
Waist circumference	X	X	X		X	X
Prior/concomitant medications	X					
Weight	X	X	X	X	X	X
Randomization			X			
FMRI Tasks						
Structural scans		X				X
Food cue task		X				X
N-back task		X				X
Behavioral Measures						
Leeds Food Preference Questionnaire (LFPQ)		X			X	X
National Institutes of Health Toolbox- Cognitive Function Battery		X			X	X
Questionnaires						
Weight and Lifestyle Inventory (WALI)	X					

Edinburgh Handedness Inventory (Short Form)	X					
Beck Depression Inventory-II (BDI-II)	X	X			X	X
Profile of Mood States (POMS) [#]		X			X	X
Food Cravings Questionnaire-State (FCQ-S) [#]		X			X	X
Eating Behaviors Questionnaire (Ratings of appetite, satiety, food preoccupation) [#]		X			X	X
Reward-Based Eating Drive Scale (RED-13)		X			X	X
Eating Inventory (EI)		X			X	X
Questionnaire on Weight and Eating Pattern-5 (QEWP-5)		X			X	X
Food Cravings Questionnaire-Trait (FCQ-T)		X			X	X
Paffenbarger Physical Activity Questionnaire (PPAQ)		X			X	X
Yale Food Addiction Scale 2.0 (YFAS 2.0)		X			X	X
Power of Food Scale (PFS)		X			X	X
Palatable Eating Motives-Revised (PEMS-R)		X			X	X
Modified Eating Patterns Questionnaire (MEPQ)			X		X	X
Eating Disorder Examination Questionnaire (EDE-Q)			X		X	X
Perceived Stress Scale (PSS)			X		X	X
Perceived Nutrition Environment (NEMS-P)			X		X	X
Brief Resilience Scale (BRS)			X		X	X

CONFIDENTIAL

This material is the property of the University of Pennsylvania.

Short Form-36 (SF-36)			X		X	X
Impact of Weight on Quality of Life-Lite (IWQOL-Lite)			X		X	X
Index of Self-Regulation (ISR)			X		X	X
Behavioral Avoidance/Inhibition Scales (BAS/BIS)			X		X	X
Adherence Measures						
Sessions attended*				X		X
Self-monitoring food records*				X		X
Additional treatment sought for weight or eating				X	X	X

*Weekly measure. ^aQuestionnaires will be sent after the screening visit and before the fMRI. ^bQuestionnaires will be distributed 10 days before scheduled fMRI and participants will be asked to complete them before the fMRI visit (except those marked with #, which will be completed at the day of the fMRI scan). ^cParticipants will be asked to complete these questionnaires at the randomization visit or via email if preferred. For participants affected by COVID-19 and subsequent mandates necessary to help mitigate the transmission of the virus (e.g., stay-at-home orders), their fMRI assessments will occur at the end of the intervention. They will have questionnaire assessments administered at week 16 and then again at the end of the intervention when they can have their fMRI scan. The randomization measures will be combined with the baseline fMRI visit.

CONFIDENTIAL

This material is the property of the University of Pennsylvania.

7 Study Intervention

WW Group Lifestyle Modification Program. The WW intervention will consist of weekly, group weight loss workshops (formerly meetings) for 16 or more weeks. Each workshop will be approximately 1 hour and include 8 to 12 participants. Participants will have access to both in-person or web-based, group meetings as well as digital tools (e.g., self-monitoring of intake, activity, and weight). The meetings will be led by a trained coach and a guide. All group sessions will be conducted at the University of Pennsylvania's Center for Weight and Eating Disorders, following the WW program. Due to the coronavirus pandemic, all non-essential visits at the University of Pennsylvania will be canceled starting March 16, 2020. As a result, each group workshop after Week 8 will be moved to a virtual video chat platform, BlueJeans. Participants have the option of calling in through video or audio. All participants will be sent standardized scales and will self-report their weight. Blood pressure will not be measured until the participants' next in-person visit. The program uses a SmartPoints® System that encourages consumption of fruits, vegetables, lean proteins, and less sugar and unhealthy fats. Participants will have their weight, blood pressure, and heart rate measured at each session. Changes in medications and adverse events will be reported privately to research staff at clinic meetings.

Wait-list control (WLC) group. Participants in the WLC group will be asked to stay weight stable and not to make changes in their eating and physical activity behaviors and not to seek treatment for weight or eating during the waiting period. They will be contacted between week 6-8 via phone by a research assistant to keep participants engaged, enhance retention and schedule their week 8 assessment visit. We will use a structured script and ask participants about any additional treatments they may have sought during the study. All WLC participants will be offered the WW intervention (as described above) after they complete the second fMRI assessment at the end of treatment.

7.1 Unscheduled Visits

Participants who miss a session will be contacted by their coach, guide, or study staff following the absence. An in-person or phone make up visit will be offered.

7.2 Subject Withdrawal

Subjects may withdraw from the study at any time without impact to their care at the University of Pennsylvania healthcare system. They may also be discontinued from the study at the discretion of the Investigator for lack of adherence to intervention or study procedures or visit schedules, AEs, or due to subject pregnancy or intention of becoming pregnant. The Investigator may also withdraw subjects who violate the study plan, or to protect the subject for reasons of safety or for administrative reasons. It will be documented whether or not each subject completes the clinical study.

Lost to follow-up: In the case of subjects who do not return to the Center for study procedures and cannot be contacted, study personnel will make vigorous and repeated attempts (minimum of 3) to contact the subject. If all attempts to contact the subject fail, that subject will be considered to be lost to follow-up and discontinued from the study.

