After participants complete the screening procedures, provide their informed consent to participate, and are enrolled into the study, they will complete two study assessment visits that include fMRIs (one at baseline and one after 16-weeks) as well as a mid-point assessment at week 8 (that does not include an fMRI).

6.3 FMRI Assessments.

Prior to randomization, participants will complete a baseline fMRI assessment that will occur up to 4 weeks before the intervention begins. They will complete another fMRI assessment between 2 weeks before the end of the intervention (or up to 1 week after the study intervention is completed). The timeframe for the follow-up assessment was selected so participants in the WW group will be actively engaged in weight loss efforts at the time of the second scanning. Participants will be compensated \$100 for each fMRI assessment visit.

Planning for the Assessment Visit. Study assessment visits will be scheduled for the morning and last approximately 3 hours (60 minutes in the fMRI scanner and 120 minutes to complete questionnaires, behavioral tasks, and physical measurements). The visits will be held at the Hospital of the University of Pennsylvania. Participants will be asked to fast (including no caffeine or alcohol) for at least 8 hours prior to the appointment to increase the stimulus salience⁴¹ and create a more homogeneous hunger state across participants. Participants will be asked to remove all jewelry and metal objects at the visit. Participants who require vision correction will be instructed to wear contact lenses or will be provided with MRsafe glasses in their prescription strength.

Imaging Procedures

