8.3 Relationship of AE to Study

- Probable: Good reasons and sufficient documentation to assume a causal relationship
- Possible: A causal relationship is conceivable and cannot be dismissed
- Unlikely: The event etiology is most likely not related to the study procedures

The PI will evaluate all unexpected events and adverse reactions.

8.4 Outcome Categories and Definitions:

- Recovered: Fully recovered or by medical or surgical treatment the condition has returned to the level observed at the first trial related activity after the subject signed the informed consent
- Recovering: The condition is improving and the subject is expected to recover from the event. This term should only be used when the subject has completed the trial
- Recovered with sequelae: As a result of the AE, the subject suffered persistent and significant disability/incapacity (e.g. became blind, deaf, paralysed). Any AE recovered with sequelae should be rated as an SAE
- Not recovered
- Fatal
- Unknown

9 Reporting of Adverse Events, Adverse Device Effects and Unanticipated Problems

All events meeting the definition of an adverse event will be collected and reported from the first trial related activity after the subject has signed the informed consent and until the end of the post-treatment follow-up period as stated in the protocol.

At a minimum the following information will be reported:

• Study identifier• Subject number• A description of the event• Date of onset	
• Current status• Whether study intervention was discontinued• The reason why the event is classified as serious• Investigator assessment of the association between the event and study intervention
--	--

Additionally all other events (unanticipated problems, adverse reactions, unanticipated adverse device effects and subject complaints) will be recorded and reported with respect to institutional and federal policies as described in the Penn Manual.

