10.1 Confidentiality

Information about study subjects will be kept confidential and managed according to the requirements of the Health Insurance Portability and Accountability Act of 1996 (HIPAA). Those regulations require a signed subject authorization informing the subject of the following:

- What protected health information (PHI) will be collected from subjects in this study
- Who will have access to that information and why
- Who will use or disclose that information
- The rights of a research subject to revoke their authorization for use of their PHI.

All electronic PHI will be maintained by using an institutionally secured and managed network drive, institutionally secured and managed devices, and institutionally approved third-party computing environments. Should PHI need to be transferred, it will be done so through the use of a Penn-approved encrypted portable drive or a Penn-approved secure encrypted file transfer solution.

In the event that a subject revokes authorization to collect or use PHI, the investigator, by regulation, retains the ability to use all information collected prior to the revocation of subject authorization. For subjects who have revoked authorization to collect or use PHI, attempts will be made to obtain permission to collect at least vital status (i.e. that the subject is alive) at the end of their scheduled study period.

Where possible, data will be entered directly into our password protected database, REDCap. All data pertaining to the study will be saved on the Center for Weight and Eating Disorders' password-protected server. Paper copies of informed consent, questionnaires, interviews, lab results, and any correspondence will be kept in the case record in locked offices.

11 Privacy

Steps will be taken to protect subject privacy. Informed consent and study procedures will be conducted in a private room, and the collection of sensitive information will be limited to the minimum necessary to achieve the aims of the project.

12 Study Monitoring, Auditing, and Inspecting

CONFIDENTIAL

This material is the property of the University of Pennsylvania.

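### Section 7.2 lets an unmasked investigator remove participants from the study for poor adherence or plan violations without securing their outcomes, which risks selective loss of the only follow-up scan

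*Protocol*

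**What the plan says.** Protocol 7.2 says participants may be "discontinued from the study at the discretion of the Investigator for lack of adherence to intervention or study procedures or visit schedules". It adds: "The Investigator may also withdraw subjects who violate the study plan". Neither adherence nor violation is given a threshold. On records, 7.2 says: "It will be documented whether or not each subject completes the clinical study". It does not ask for the reason or date of a removal. The lost-to-follow-up paragraph uses the same expression: "that subject will be considered to be lost to follow-up and discontinued from the study".

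Other relevant text:

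- Section 4.1: neither participants nor investigators are masked.
- Section 6.2.2, on imaging: "they will complete two study assessment visits that include fMRIs (one at baseline and one after 16-weeks". For participants affected by COVID-19 the second scan moves to the end of the extended intervention, but there are still two scans.
- Section 6.5: "After individuals in the WLC group complete their second fMRI assessment, they will be offered the WW treatment".
- Section 7, wait-list paragraph: during the wait these participants are asked to keep their weight stable, leave eating and activity unchanged, and seek no weight or eating treatment. A scripted call asks about other treatment.
- Section 9: adverse event reports include "Whether study intervention was discontinued", so the protocol does have the narrower idea of stopping the program.
- Section 10.1, only for revoked authorization: data already collected may be used, and "attempts will be made to obtain permission to collect at least vital status".
- SAP, Food Cues and Hippocampal Volume: mixed models of baseline and follow-up. Maximum likelihood is named for hippocampal volume.

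**The concern.** The rule can remove people after randomisation on the judgement of someone who knows their arm, and what it ends is study participation, not only the program. The grounds are not the same in both arms. Before the second scan, adherence to WW can be judged only in the WW arm. A wait-list participant who loses weight or seeks treatment elsewhere breaks a condition that the WW arm does not have, and that can count as violating the study plan. The study-procedure and visit-schedule grounds apply to both arms.

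The food-cue, N-back and hippocampal primary endpoints (section 3.1.1) are changes that need the second scan. A participant removed before it has a baseline image and nothing else. Section 4.1 describes weight loss as a mechanism expected to bear on the fMRI results, so removing people for behaviour linked to weight could select on the outcome. Appetite measures are less exposed, because week 8 data may be in hand, and week 16 data too where the intervention was extended.

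**Working it through.** **The text.** The plan gives no figure to reproduce on this point. Sections 7.1 (make-up visits), 7 (wait-list call), 7.2, 9 and 10.1 are the places where follow-up after removal could have been secured. The first two concern missed sessions and engagement, section 9 concerns event reports, and 10.1 covers revoked authorization only. None provides for the follow-up scan or questionnaires after an investigator-initiated removal.

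**Illustration of size.** From the documents: 30 per arm and one follow-up scan. All else is assumed: no true effect; change has SD 1 in each arm; adherence correlates with change at c = 0.3 or 0.5 through shared causes, since with no true effect it cannot arise through the program; the least adherent fraction f = 10, 20 or 30% of WW (3, 6 or 9 people) lose the second scan; no wait-list participant does.

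1. Completer bias = c × φ(q_f)/(1−f), where q_f is the f quantile of the standard normal. For f = 20%: φ(−0.842) = 0.280 and 0.280/0.8 = 0.350, giving 0.105 SD at c = 0.3 and 0.175 SD at c = 0.5.
2. Maximum-likelihood mixed model keeping all baseline scans: if adherence depends on change, baseline explains (1−r)/2 of the variance of change, where r is the scan-rescan correlation. The bias left is completer bias × (1+r)/2, that is 75% at r = 0.5 and 95% at r = 0.9.
3. If half of those removed would have missed the scan anyway (taken as the least adherent half), the rule itself adds [bias(f) − bias(f/2)] × (1+r)/2.

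| c | removed | completer bias (SD) | ML bias, r = 0.5 to 0.9 | added by the rule, ML |
|---|---|---|---|---|
| 0.3 | 3 | 0.058 | 0.044–0.056 | 0.02 |
| 0.3 | 6 | 0.105 | 0.079–0.100 | 0.03–0.04 |
| 0.3 | 9 | 0.149 | 0.112–0.142 | 0.05–0.06 |
| 0.5 | 3 | 0.097 | 0.073–0.093 | 0.03–0.04 |
| 0.5 | 6 | 0.175 | 0.131–0.166 | 0.06–0.07 |
| 0.5 | 9 | 0.248 | 0.186–0.236 | 0.08–0.11 |

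Simulation of the two-scan maximum-likelihood estimate, 20,000 trials per cell, agrees with the ML column within 0.007 SD. For scale, the standard error with 30 per arm is √(2/30) = 0.258 SD. Simulated type I error for the ML analysis, over all three removal counts:

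- c = 0.3: 5.1–7.4% at .05 and 1.0–1.8% at .01, the food-cue threshold.
- c = 0.5: 5.8–12.6% at .05 and 1.2–3.9% at .01.

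**Both arms** (c = 0.5, r = 0.7, ML). Six removed in each arm with the same selection: about 0. Six WW and three wait-list with the same selection: 0.07 SD. If the three wait-list removals select the other way, for instance people who improved after seeking treatment, the biases add: 0.149 + 0.083 = 0.23 SD. The documents give no reason to prefer any of these patterns.

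**The case against.** Several points on the other side stand.

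- The clause is permissive and common in protocols, and nothing shows it was used. Make-up visits and the retention call point to an intent to keep people in, and the Introduction says noncompliance will be documented.
- A reader might infer from the shared wording with the lost-to-follow-up paragraph that removal must end outcome collection. That parallel proves little, because people lost to follow-up cannot be reached in any case. What stands is that 7.2 does not use the narrower idea found in section 9, and that nothing available provides for continued collection.
- A reader might infer that only WW participants can be removed on an arm-specific ground, so that any bias favours WW. The documents do not support this. The wait-list conditions are arm-specific too, and removals there could reduce, reverse or add to a bias.
- Every input to the illustration is assumed, including a link between adherence and change with no true effect. On the ML basis the bias stays below one standard error.
- Part of each document was not available, so silence on analysis sets and missing data is weak evidence. A reader should not conclude that the plan has no intention-to-treat analysis.
- The SAP is written in the past tense, so follow-up may be over.

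These points limit the size and certainty of the problem. They do not supply the missing provision for outcomes.

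**Conclusion.** The point holds as a risk of bias. Section 7.2 as written allows arm-aware removal from the study, on grounds that differ by arm, with no available provision to obtain the one follow-up scan on which the imaging primary endpoints rest. A mixed model can recover only the part of the selection that baseline predicts. On the assumed inputs above, ML bias is about 0.04–0.24 SD of change. The part due to the rule itself, if half would have missed the scan anyway, is about 0.02–0.06 SD at c = 0.3 or 0.03–0.11 SD at c = 0.5.

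A reader might go further and say that the result is biased towards WW. The documents do not support that: they report no number removed, no reasons and no arm split. The firm parts are the wording of 7.2 and the reporting of removals by arm. The sensitivity analysis is conditional on missing scans and on what the unavailable text already contains. Confidence is medium.

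**What to change.** 1. In 7.2, state that lack of adherence or departure from the study plan does not by itself end outcome follow-up. These participants are still offered the planned follow-up scan and questionnaires unless they withdraw consent or scanning is unsafe. Leave safety and pregnancy withdrawals, and the rules on who receives the program, unchanged.
2. Record the reason and date of each investigator-initiated removal, and report them by arm.
3. Unless text not available here already does so, analyse all randomised participants as assigned. If follow-up scans are missing, add a sensitivity analysis that shifts missing changes separately in each arm, in both directions, over a stated range. As an example only: with 6 WW and 3 wait-list scans missing and shifts of up to ±0.5 SD, the estimate moves by at most 0.5 × 6/30 + 0.5 × 3/30 = 0.15 SD.

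Cost: a few scans already planned for the 60 participants, a reason-and-date field, one extra analysis, and a possibly diluted effect estimate because poor adherers stay in. If follow-up is already finished, item 1 recovers no scan and only items 2 and 3 apply.
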